3.3.2. Handling Missing Data

For the prospective cohort, unless specified otherwise in each objective, there will be no imputation of missing data. Subjects from the prospective arm with missing data will not be included in the analysis. The number of subjects included in each analysis will be reported so that the potential impact of missing data can be assessed. Note that the issue of partial dates has been preemptively accounted for such that the minimum requirement for dates in each variable category has been specified.

It is not expected that there will be a need for imputation for missing data in the historical control arm due to the large pool of historical control candidates. However, the extent of missing data in the candidate pool will be evaluated and addressed if necessary with multiple imputation procedures. Depending on whether the nature of the missing data is monotone or random, either the monotone or Markov chain Monte-Carlo (MCMC) multiple imputation methods will be employed.

3.3.3. P-Values

The statistical test for the primary objective will be performed at two-sided $\alpha=0.05$. All reported p-values ≥ 0.0001 will be rounded to four decimal places. P-values <0.0001 will be displayed as “ <0.0001 ”.

3.3.4. Analysis Data Sets

The primary analysis will be evaluated for the evaluable population (EP), which will consist of all enrolled subjects who receive study drug and complete all study phases as per protocol. The data from the subjects in the prospective arm who were enrolled but who did not receive study drug (ITT) will be summarized separately, and the relevant details thereof – particularly the rationale for not receiving study drug despite being enrolled – analyzed and reported descriptively.

The propensity score matching procedure will combine data collected from the prospective arm (Furoscix Infusor) and data collected from the claims-based historical control arm. The data set for the latter will be derived from a preliminary analysis of claims for patients with HF who were seen in the emergency department for HF-related causes at any time between the years 2012 to 2017 (later updated to most recent data until 2019). This data set will constitute the candidate pool from which propensity-matched controls will be drawn, and the data elements will include all background demographic and baseline clinical data elements collected for the prospective arm except for lab values.

[figure not shown]

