Prior to leaving the emergency department on Day 0, the subject and/or caregiver will be trained by the study staff on how to prepare the study product and apply it to their abdomen and remove it once the infusion is completed. The initial dose of the study product may be administered on the day of enrollment. Some subjects may not require their initial dose until the next day. Doses will be provided to the patient for self-administration or administration by a caregiver in the home setting as directed by the investigator or study staff. No more than 7 doses of Furoscix are permitted during the 30-day study period unless approved by the medical monitor. Planned in-person follow-ups include a clinic visit occurring between Days 2-4 and a clinic visit on Day 30±3 days. Scheduled remote follow-ups conducted by telephone by a HF nurse, or designee, will occur on Days 1 and 7, and one call between Days 14-21. Unscheduled at-home telephone calls and unscheduled in-clinic visits may be performed if felt clinically indicated by the study team or the clinical provider.

The Follow-Up Phase will occur on Day 30±3 days for a post treatment follow-up visit completing Subjects' study participation.

Refer to [Figure 2](#) for an overview of study phases and procedures. Note that the depiction in [Figure 2](#) of Furoscix administrations after Day 1 is for demonstration purposes. Again, the investigator can prescribe additional Furoscix dosing and administration at his/her discretion as long as this does not conflict with safe use practices as defined in this protocol and supplementary materials.

Figure 2: Study Phases and Procedures

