3.3. Important Considerations

3.3.1. Defined Populations applicable to the prospective arm

3.3.1.1. Intent to Treat (ITT) Population – Subjects who meet all of the inclusion criteria and none of the exclusion criteria and whose IRB-approved informed consent form has been signed and dated by all required parties.

3.3.1.2. Safety Population (SP) – Subset of the ITT received a dose of FUROSCIX (whether they completed or did not complete all study phases through 30-day follow up).

3.3.1.3. Evaluable Population (EP) – Subset of the SP who completed all the study phases as per the protocol.

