3.5.2. Step 1: Determining the Initial Target Sample Size

Although this is an adaptive clinical trial with sequential cohort design whereby the final sample size will ultimately be determined by the prespecified interim analyses, it was necessary for trial planning purposes to generate an estimated final sample size based purely on a priori assumptions.

Based on an average hospital cost of a patient hospitalized for \leq 72 hours with a primary diagnosis of HF (Diagnosis Related Group Code 291, 292 and 293) of \$8,600 (standard deviation: \$3,045), 68 patients (34 evaluable patients in each group) are required to have an 80% chance of detecting a decrease in hospital costs to \$6,500 at a significance level of 5%. The target sample size of the Furoscix cohort will initially be N=34 subjects.

Re-assessment of the sample size will be conducted once 34 subjects in the Furoscix cohort complete all study phases as per protocol (matched 1:1 to 4:1 to propensity matched controls to generate comparisons) by using a group sequential design and testing to allow for stopping. It is not expected that the sample size for the Furoscix Infusor arm would exceed N=75, but the maximum value cannot be definitively stated until the analysis at N=34 is completed.

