3.5.3. Step 2: Produce Candidate Pool for Historical Cohort

EPI-Q will produce a candidate pool from which historical controls will be drawn via propensity match for comparison against the Furoscix Infusor cohort. This candidate pool will be comprised of HF-patient lives contained in the Marketscan Commercial Claims and Encounters (CCAE) and Medicare Supplemental Database. This pool will contain HF patients who will be characterized by binary indicators consistent with the demographic and background clinical variables (except laboratory tests) that are collected for the Furoscix Infusor arm (Appendix B).

Initially, the historical cohort will be created using the Marketscan Commercial Claims and Encounters (CCAE) and Medicare Supplemental Database for the years 2015-2017. The historical cohort will be later updated post acquisition of latest data up to year 2019.

The following inclusion criteria will be applied to identify patients with worsening HF:

1. Inpatient claims coded with an HF (ICD-9/ICD-10) diagnosis codes in primary position on the claim
2. Worsening HF defined by all admissions coded with a diagnosis-related group (DRG) for HF (291, 292, or 293)
3. Length of Stay 1-3 days
4. Service Category included ED Visit
5. Age 18-80 years
6. Continuous enrollment for 1 year before and 3 months after the index date
7. Background therapy including oral furosemide equivalents daily (Torsemide or Bumetanide)

First qualifying claim, where all the eligibility criteria is met, will be defined as the index date. Patients will be excluded if one of the following exclusion criteria is met:

1. Presence of diagnosis code for a complicating condition, other than HF (e.g. MI, pneumonia) as identified from the prospective arm data before final matching
2. Presence of diagnosis or procedure code for acute renal failure or Dialysis
3. Estimated Creatinine Clearance (CrCl) <30 (indicated by presence of diagnosis code for chronic kidney disease stage 4/5, ESRD or renal failure).

For the patients that meet all the eligibility criteria, the following demographic and baseline characteristics (i.e., candidate variables for propensity score calculation) will be determined and reconciled between the prospective study and historical controls' databases (i.e., only variables that can be consistently defined will be analyzed):

- Integer age
- Sex
- Geographic region (Northeast, North Central, South, West, Unknown)

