3.5.5. Step 4: Interim and Final Analysis with Propensity Match

Interim analyses to determine whether efficacy or futility has been reached will be conducted in a prespecified manner at N=10 and N=34 in the evaluable population. Additional interim analyses may be conducted as needed. Note that the enrollment for the prospective arm will continue as the interim analysis is carried out up to N=34, at which point re-assessment of sample size will be conducted.

For the interim analyses, the comparators will be historical controls drawn from the aforementioned candidate pool using a 1:1 to 4:1 propensity score matched approach. The propensity score matching process will be conducted via a caliper-based mechanism that allows for an iterative matching approach that will maximize the efficiency of the match protocol using methods reported by Millar and Pasta 2010.

The primary final analysis will include a 1:1 to 4:1 propensity match using the identical algorithm produced in the last interim analysis. Additional final analyses will explore the impact of increasing the ratio of cases to controls up to a 1:10 match. Note that the aforementioned matching method will be applied so that no Furoscix subjects will be dropped from the analysis due to the lack of a suitable match or matches.

The propensity scores (1 for each case and control) will be generated with the SAS PROC LOGISTIC function to produce a multivariate logistic regression. The propensity score is the predicted probability of receiving the Furoscix Infusor treatment. Both automatic stepwise and manual variable selection will be evaluated.

Criteria for propensity score matching are listed below:

- In addition to requiring that the absolute difference between the treatment arm propensity score and the control patient's propensity score be no larger than 0.01, exact sex, the absolute difference in age could be no larger than 5 years, and time between time zero visits could be no more than 730 days (or 1095 days). These key measure requirements reduced the data set substantially to a data set of potential matches.

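### The primary cost test keeps only dosed Furoscix subjects who finish Day 30 follow-up, controls need 3 months of enrollment for a roughly 30-day outcome, and no all-dosed cost comparison is planned

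*SAP*

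**What the plan says.** **Furoscix arm.** SAP 3.3.4 places the primary analysis in the evaluable population, "which will consist of all enrolled subjects who receive study drug and complete all study phases as per protocol". SAP 3.3.1 defines that set as a "Subset of the SP who completed all the study phases as per the protocol". The Safety Population is everyone dosed, "whether they completed or did not complete all study phases through 30-day follow up", which indicates that the phases run to the 30-day follow-up. Protocol 6.2 agrees: "The Follow-Up Phase will occur on Day 30±3 days for a post treatment follow-up visit". SAP 3.3.2 adds that "Subjects from the prospective arm with missing data will not be included in the analysis". SAP 3.5.3 relaxes this only for baseline covariates, through an unknown category or mean imputation.

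**Looks.** Sample size is re-assessed "once 34 subjects in the Furoscix cohort complete all study phases as per protocol" (SAP 3.5.2), and the interim analyses "will be conducted in a prespecified manner at N=10 and N=34 in the evaluable population" (SAP 3.5.5).

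**Controls.** SAP 3.5.3 requires "Continuous enrollment for 1 year before and 3 months after the index date" and states no exception for death.

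**Outcome window.** SAP 3.5.3.1 counts costs over 30 days from the start of the worsening episode. The endpoint wording in SAP 3 and 3.5.1 runs through 30 days after discharge.

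**Other uses of the data.** The Safety Population is used only for descriptive safety summaries (SAP 3.4). Enrolled but undosed subjects are only described (SAP 3.3.4). The extra final analyses vary the matching ratio, not the population (SAP 3.5.5). The primary endpoint itself is worded for subjects treated, with no completion condition (Protocol 3.2.1, SAP 3).

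**The concern.** Whether a subject completes follow-up is known only after treatment starts and may be related to cost. Protocol 4.3 discontinues subjects for withdrawal of consent, safety, non-compliance or investigator discretion, and a subject who dies before Day 30 cannot complete. Leaving these people out changes the question from the cost of treating patients with Furoscix to the cost among those who got through the month.

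Controls are selected on a different later event, namely staying enrolled for about three months. Patients with complete 30-day costs are dropped if they leave the plan or die between the end of the window and month three.

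The propensity score uses variables measured at or before time zero, so it cannot balance either selection. The two filters may push in opposite directions. The planned counts of subjects per analysis (SAP 3.3.2) and of disposition (Protocol 8.2) would show how many dosed subjects are missing, but not whether the cost difference depends on them. The same restriction governs the stopping looks and the sample-size re-assessment.

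**Working it through.** **Inputs from the documents** (Protocol 8.1, SAP 3.3.3 and 3.5.2): control mean $8,600, Furoscix mean $6,500, SD $3,045, 34 evaluable per group, 80% power, two-sided 5%.

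**The plan's own figure.** n = 2 × [3,045 × (1.960 + 0.842) / 2,100]² = 33.0 per group by the normal formula, 34 after rounding up. The t-test solution is 33.99, so 34. The stated sample size reproduces and is not at fault.

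**Assumptions.** The documents give neither a non-completion rate nor a cost for non-completers. I take 34 completers at exactly $6,500 and restore k dosed subjects at cost c each. The values of c are $3,250 (half of $6,500), $8,600 (the control mean) and $17,200 (twice $8,600).

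- Shift in the Furoscix mean = k(c − 6,500)/(34 + k).
- Furoscix SD = √{[33 × 3,045² + (34k/(34 + k))(c − 6,500)²]/(33 + k)}.
- Controls: n = 34 + k, mean $8,600, SD $3,045. Unpaired pooled t-test with 2(34 + k) − 2 df.

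| c | k | Shift | Furoscix SD | Difference | Nominal p |
|---|---|---|---|---|---|
| none | 0 | 0 | $3,045 | $2,100 | 0.0059 |
| $3,250 | 1 | −$93 | $3,050 | $2,193 | 0.0037 |
| $3,250 | 6 | −$488 | $3,038 | $2,588 | 0.0003 |
| $8,600 | 1 | +$60 | $3,021 | $2,040 | 0.0064 |
| $8,600 | 6 | +$315 | $2,902 | $1,785 | 0.0089 |
| $17,200 | 1 | +$306 | $3,503 | $1,794 | 0.0253 |
| $17,200 | 2 | +$594 | $3,863 | $1,506 | 0.0705 |
| $17,200 | 6 | +$1,605 | $4,777 | $495 | 0.58 |

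The extreme shifts are −488/2,100 = −23% and +1,605/2,100 = +76% of the planned effect. Nominal p reaches 0.05 with two restored subjects at about $15,800 each, or with one at about $21,400.

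**False-positive side.** Suppose there is no true difference (both all-dosed means $8,600) and a fraction q of dosed subjects costing C each is excluded. The apparent saving is q(C − 8,600)/(1 − q). Take C = $15,100, which is $6,500 plus one $8,600 admission. With q = 10% the saving is 0.10 × 6,500/0.90 = $722. The standard error at 34 versus 34 is 3,045 × √(2/34) = $739, so the chance of a significant result favoring Furoscix is Φ(722/739 − 1.96) ≈ 16%, against a nominal 2.5%. At q = 5% it is about 7% (saving $342), and at q = 20% about 60% (saving $1,625).

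**Limits of these figures.** They ignore the matching and the O'Brien-Fleming boundaries. If the maximum were 75, O'Brien-Fleming-type spending at 34/75 is 2 − 2Φ(1.96/√(34/75)) = 0.0036, so even the unaltered 0.0059 would not cross at that look. The figures show sensitivity, not that a stopping decision would change.

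**Control window.** Take index as admission and 3 months as about 91 days. A stay of 1 to 3 days plus 30 days ends on day 31 to 33, and 30 days from episode start ends on day 30. The enrollment rule therefore runs 91 − 33 = 58 to 91 − 30 = 61 days past the outcome.

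**The case against.** The strongest reply concerns size. Of the three cost levels tabulated, only $17,200 takes nominal p past 0.05, and that cost is an assumption. HF readmission alone does not remove anyone: Protocol 3.1 stops Furoscix in that case, not participation. Those who leave are deaths, withdrawals and removals, whose costs are unknown and may be low. The p-values are unpaired and nominal, while the plan uses a paired test and group sequential boundaries. The effect of the control filter is not quantified at all. All of this stands, and it is why the figures are offered only as a range.

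A second reply is that SAP 3.5.3.1 estimates costs for each patient and the protocol endpoint covers subjects treated, so an all-dosed comparison might be implied. The estimates would make one feasible, but SAP 3.3.4 assigns the primary test to completers and no section plans another. The gap between endpoint wording and analysis set adds to the problem.

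Third, the codebook and case report form (SAP Appendices A and B) were not available to read and might define completion or handle deaths. They could clarify terms, but would not displace the rules stated in SAP 3.3.4 and 3.5.3.

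Fourth, being dosed is itself a post-enrollment condition. That is true, but it matches an endpoint defined for treated subjects.

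Finally, Protocol 4.3 asks that withdrawn subjects have the follow-up assessments where possible. Whether they then count as completers is not stated, so the size of the excluded group cannot be fixed in advance.

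**Conclusion.** The concern holds. As written, the primary superiority test and both looks exclude dosed non-completers, controls are selected on a longer and different post-index condition, and no cost comparison covers all dosed subjects. That this selection differs by arm follows from the text and needs no assumption.

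The size of the resulting bias is not known, and neither is its net direction. Under the assumed costs the Furoscix mean could move by anything from 23% of the planned effect in favor of Furoscix to 76% against it. With about 34 subjects, one or two costly exclusions can matter, while exclusions near the control mean change little. Because this defines the headline population of a small, unblinded, externally controlled study and is inexpensive to correct, it should be changed before any cost comparison is run.

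**What to change.** 1. Make the Safety Population (all dosed subjects) the primary cost set and count the N=10 and N=34 looks in it. Keep the evaluable population as a sensitivity analysis, with completion of all study phases defined, including the status of withdrawn subjects who have the follow-up assessments.
2. Count utilization to Day 30 or death from follow-up contacts and medical records, extending the record check in Protocol 6.2.6 from HF-related to all-cause events.
3. State in advance the rule for days that neither source covers. One option is to impute events at the rate seen in the other dosed subjects, bounded by zero events and by one HF admission at the SAP 3.5.3.1 benchmark.
4. Report deaths beside the cost result, so that an early death does not read as a saving.
5. Reconcile the two outcome windows (episode start in SAP 3.5.3.1, post-discharge in the endpoint). Then shorten the control post-index enrollment rule to match: 30 days, or the index stay plus 30 days (about 31 to 33). Keep controls who die within the window if the claims data record death.

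**Cost.** SAP wording, one changed claims filter, a wider record check and look-up for non-completers. Post-withdrawal assessments, HF-related record verification and event-based costing are already planned. The downsides are partly imputed costs for some subjects, and records that may be unavailable after consent is withdrawn.

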3.3.5. Trial Design

A group sequential design is being employed to allow for stopping due to futility or efficacy. This design includes the following general steps (cite SAS manual for group sequential designs):

1. Specify the statistical details of the design, including the null and alternative hypotheses (null hypothesis being that there is no difference in 30-day HF-related direct medical costs between the Furoscix Infusor and historical control arms), a test statistic for the hypothesis test, the Type I and II error probabilities, a stopping criterion, the total number of stages, and the relative information level at each stage.
2. Compute the boundary values for the trial based on the specifications in Step 1 and compute the sample size required at each stage for the specified hypothesis test.
3. At each stage, collect additional data with the required sample sizes. This includes the data collected at the current stage in addition to the data collected at previous stages.
4. At each stage, analyze the available data and compute the test statistic.
5. At each stage, compare the test statistic with the corresponding boundary values. The trial will stop to reject or accept the hypothesis, or it will continue to the next stage.
6. Once the trial stops, parameter estimates, confidence limits for the parameter, and a p-value for the hypothesis test are computed.

Below is a depiction of a hypothetical 4-stage design with two-sided testing.

Figure 1. Boundaries for Two-Sided Group Sequential Test

The four stages of the hypothetical trial presented in the preceding figure are indicated by vertical lines labeled 1, 2, 3, and 4. With early stopping to reject the null hypothesis, the lower rejection boundary is constructed by connecting the lower critical values for the stages. Similarly, the upper rejection boundary is constructed by connecting the upper critical values for the stages. The horizontal axis indicates the sample size for the group sequential trial, and the vertical axis indicates the values of the test statistic on the standardized Z scale. At each interim stage, if the test statistic falls into a rejection region the trial stops and the null hypothesis is rejected. Otherwise, the trial continues to the next stage. At the final stage the null hypothesis is rejected if Z falls into the rejection region. Otherwise, the null hypothesis is not rejected. In the figure, the test statistic falls into the rejection region in stage 3 and the null hypothesis is rejected.

An important concern with group sequential designs is correcting for multiplicity caused by conducting multiple, sequential correlated statistical tests thereby increasing the probability of Type 1 error. To correct for this issue one must preemptively define local significance levels for each statistical test and define the stopping boundaries. Herein, we will employ the O'Brien and Fleming error spending function to distribute the overall Type 1 error rate across the interim and final analyses. Because the O'Brien and Fleming approach includes an increase in the local significance level with each subsequent analysis (i.e., with each stage) it is considered among the more conservative approaches.

3.4. Safety Objective

The safety analysis includes assessment of adverse events (AEs) and device performance. The safety of Furoscix will be monitored during the trial, and identified safety issues (including AEs, SAEs, and adverse reactions) will be summarized descriptively in the safety population for the Furoscix cohort.

The incidence (number and percentage of subjects) of adverse events will be presented overall and by MedDRA System Organ Class and Preferred Term for the Furoscix cohort. Reactions at the infusion site and frequency of these reactions will be reported. This analysis will be repeated for serious adverse events, for treatment-related adverse events, and for adverse events leading to premature study withdrawal.

